2.2.7 End of Trial Definition

End of the trial is defined as the date of the last visit or last scheduled procedure for the last patient, including the continued-access follow-up visit, if applicable.

2.3 Study Endpoints

2.3.1 Primary Endpoint

The primary endpoint of this study is OS, defined as the time from date of Randomization to death due to any cause.

2.3.2 Secondary Endpoints

The secondary endpoints of the study include:

- PFS is defined as the time from date of Randomization to the earlier of first documentation of definitive disease progression (the initial PD that was confirmed by the consecutive scan) or death due to any cause.
- ORR is defined as the proportion of patients who achieve a CR or PR as assessed by RECIST v.1.1.
- DoR is defined as the time from the date of the first documentation of objective tumor response (CR or PR) to the date of the first documentation of objective tumor progression or death due to any cause, whichever occurs first.
- 1-year OS rate is defined as the survival rate as estimated using the Kaplan-Meier method at the end of the first year.

2.3.3 Exploratory Endpoints

Baseline and change from baseline in immune and molecular biomarkers and their relationship to clinical efficacy endpoints will be explored.

In addition to baseline and change from baseline in the EORTC QLQ-C30 and EQ-5D-5L, time to deterioration in patient-reported symptoms and functioning will be explored using symptom items that correspond with the TEAE profile (eg, fatigue, anorexia, and nausea/vomiting) as well as the subscales for functioning and HRQoL.

2.3.4 Trial Duration

Approximately 36 months (screening, enrollment, and study completion). Twenty-five months for patient enrollment, opportunity to have at least 6 months of treatment or until PD by RECIST v.1.1, 2-months follow-up, and 2 months of data auditing and analysis.

3.0 STUDY POPULATION

3.1 Patient Selection Criteria

Investigators will maintain a screening log of all potential study candidates that includes limited information about the potential candidate (eg, initials, age, and gender), date, and outcome of the screening process (eg, enrolled into study, reason for ineligibility, or refusal to participate).

3.1.1 Inclusion Criteria

To be eligible for this study, patients must fulfill all of the following inclusion criteria:

1. The presence of metastatic pancreatic adenocarcinoma plus 1 of the following:
 - a. Histological diagnosis of pancreatic adenocarcinoma confirmed pathologically, OR
 - b. Pathologist-confirmed histological/cytological diagnosis of adenocarcinoma consistent with pancreas origin in conjunction with either:
 - i. The presence of a mass in the pancreas, OR
 - ii. A history of pancreatic adenocarcinoma.
2. Measurable disease per RECIST v.1.1.
3. Patient must have documented tumor progression during or following a gemcitabine-containing regimen for the treatment of metastatic disease. Diagnosis of progression (by computed tomography [CT] or magnetic resonance imaging [MRI] scan or clinical progression) must be within 28 days prior to Randomization.
4. Only 1 prior gemcitabine-containing therapy and no other prior therapies for metastatic disease.
5. Male or non-pregnant, non-lactating female, ≥ 18 years or age.
 - a. If a female patient is of child-bearing potential, as evidenced by menstrual periods, she must have a negative serum pregnancy test (beta-human chorionic gonadotropin [β -hCG]) documented prior to the first administration of study drugs.
 - b. If sexually active, the patient must agree to use contraception considered adequate and appropriate by the Investigator (see [Appendix H](#) for full list of acceptable methods) during the period of administration of study drugs. In addition, male and female patients must utilize contraception after the end of the treatment as recommended in the individual drugs comprising FOLFOX product's Summary of Product Characteristics or Prescribing Information provided in the Pharmacy Manual and the Clinical Trial Facilitation Group, provided in [Appendix H](#).

6. Provide signed written informed consent.
7. ECOG PS of 0–1.
8. Patient must have completed prior chemotherapy and any investigational therapy at least 2 weeks (washout period) prior to Randomization and recovered from toxicity to Grade 1 or baseline.
9. Willingness and ability to comply with study requirements.
10. Patient has adequate organ function by the following laboratory assessments at baseline (obtained ≤ 21 days prior to Randomization):

Hematologic

- Platelets $\geq 100 \times 10^9/L$
- Hemoglobin ≥ 9.0 g/dL
- Absolute Neutrophil Count (ANC) $\geq 1.5 \times 10^9/L$
- Patient has acceptable coagulation values obtained ≤ 21 days prior to Randomization as demonstrated by prothrombin time (PT) and partial thromboplastin time (PTT) $\leq 1.5 \times$ upper limit of normal (ULN) (if on Coumadin, patient must be changed to LMWH or on Factor II or Xa anticoagulant with a $t_{1/2}$ of less than 24 hours).

Hepatic

- Aspartate transaminase (AST)/alanine transaminase (ALT) $\leq 3 \times$ ULN (if liver metastases are present, $\leq 5 \times$ ULN)
- Alkaline phosphatase $\leq 2.0 \times$ ULN (if liver metastases are present, $\leq 5 \times$ ULN)
- Total bilirubin $\leq 1.5 \times$ ULN
- Albumin ≥ 3.0 g/dL

Renal

- Serum creatinine <2.0 mg/dL or calculated creatinine clearance ≥ 60 mL/min for patients with serum creatinine levels above the institutional normal value. If using creatinine clearance, actual body weight should be used for calculating creatinine clearance (eg, using the Modification of Diet in Renal Disease [MDRD] formula, (Levey, Coresh et al., 2006)). For patients with a body mass index (BMI) >30 kg/m², lean body weight should be used instead.

11. Patient must have a life expectancy of ≥ 4 months in the opinion of the Investigator.

3.1.2 Exclusion Criteria

Patients meeting any of the following criteria are not eligible for study participation:

1. Diagnosis of pancreatic islet neoplasm, acinar cell carcinoma, non-adenocarcinoma (ie, lymphoma, sarcoma), adenocarcinoma originating from the biliary tree, or cystadenocarcinoma.
2. Patient has experienced a decrease in ECOG PS (Appendix E) between Screening visit and within 72 hours prior to Randomization.
3. Patient on Coumadin and not willing to change to LMWH or oral Factor II or Xa inhibitor with $t_{1/2}$ of less than 24 hours.
4. Patient has received prior treatment with AM0010 or a platinum-containing regimen.
5. Patients who were intolerant to gemcitabine-containing regimens (unable to receive at least 8 weeks of treatment).
6. History of prior malignancy, except for adequately treated in situ cancer, basal cell, squamous cell skin cancer, or other cancers (eg, breast and prostate) for which the patient has been disease-free for at least 3 years. Patients with prior cancer that is adequately controlled per the judgement of the Investigator will not be excluded from the study.
7. Any serious medical condition, laboratory abnormality, psychiatric illness, or comorbidity that, in the judgment of the Investigator, would make the patient inappropriate for the study
8. Patients with abnormal electrocardiogram (ECG) at baseline (QT or QTc interval >450 ms for males; QT or QTc interval >470 ms for females) will be excluded from this study.
9. Serious systemic fungal, bacterial, viral, or other infection that is not controlled or requires intravenous antibiotics.

10. Known history of positivity (regardless of immune status) for human immunodeficiency virus (HIV).
11. Known history of chronic active or active viral hepatitis A, B, or C infection.
12. Clinically significant bleeding within 2 weeks prior to Randomization (eg, gastrointestinal [GI] bleeding or intracranial hemorrhage).
13. Pregnant or lactating women.
14. Patients with a history of immune-mediated neurological disorders such as multiple sclerosis, Guillain-Barré, or inflammatory central nervous system (CNS)/peripheral nervous system (PNS) disorders.
15. Myocardial infarction within the last 6 months prior to Randomization, symptomatic congestive heart failure (New York Heart Association Classification >Class II, [[Appendix F](#)]), unstable angina, or unstable cardiac arrhythmia requiring medication.
16. Clinically significant ascites defined as requiring ≥ 1 paracentesis every 2 weeks.
17. Major surgery, defined as any surgical procedure that involves general anesthesia and a significant incision (ie, larger than what is required for placement of central venous access, percutaneous feeding tube, or biopsy) within 28 days prior to Randomization or anticipated surgery during the study period.
18. Prior history of receiving immune checkpoint inhibitors (anti-CTLA4, anti-PD1, anti-PD-L1).
19. Peripheral neuropathy (>Grade 1).
20. Known history of dihydropyrimidine dehydrogenase deficiency (DPD).
21. Prior history of previous radiation therapy or surgery for the treatment of pancreatic cancer (eg Whipple or pancreatectomy, etc.). Prior history of receiving gemcitabine or any other chemotherapy in the adjuvant setting.

3.2 Randomization

All patients must personally sign, date, and receive a copy of the Informed Consent Form (ICF) before any study-specific screening procedures are performed. Standard medical practice procedures (CT, MRI, physical examination, or blood tests) performed within the specified screening period may be used for Screening if conducted within 21 days prior to Randomization. Patient eligibility will be established at the conclusion of the screening evaluations.

All patients who sign an informed consent will be identified by a unique patient number. This number will be used to identify the patient throughout the clinical study and must be used on all study

documentation related to that patient. The patient identification number must remain constant throughout the entire clinical study.

3.3 Rescreening Criteria

Re-screening may be allowed. Patients who are re-screened after 30 days must be re-consented with a new screening number and repeat the screening assessments. For patients re-screened within 30 days, assessments with results that would exclude the patient will need to be repeated.

4.0 STUDY TREATMENT DISCONTINUATION AND STUDY DISCONTINUATION

4.1 Study Treatments Discontinuation

AM0010 or any of the components of FOLFOX can be discontinued for any of the following reasons.

- Adverse events
- Pregnancy
- Investigator decision to discontinue the patient from the components of the study treatments, in consultation with Lilly Medical Monitor
- Clinical disease progression
- Radiographic disease progression by RECIST v.1.1
- Intercurrent illness that would, in the judgment of the Investigator, affect assessments of clinical status to a significant degree
- Initiation of new anti-neoplastic therapy in the absence of tumor progression
- Patient request to discontinue study treatments
- Withdrawal of consent
- Death
- Discontinuation of the study at the request of Lilly, a regulatory agency, or an Institutional Review Board or Independent Ethics Committee (IRB/IEC)
- Poor or non-compliance with study procedures
- Major protocol violation
- Loss to follow-up

Should this occur, the corresponding study drugs completion CRF should be entered to document the reason for discontinuation. In addition, the patient should continue with the rest of the treatment regimen and the study-related procedures per the protocol.

4.2 Study Discontinuation

Patient study participation may be ended due to any of the following reasons:

- Withdrawal of consent
- Death
- Discontinuation of the study at the request of Lilly, a regulatory agency, or an IRB/IEC
- Loss to follow-up

5.0 AM0010 AND FOLFOX TREATMENT

All study investigational product administration will occur under medical supervision or by the patient after proper instruction by medical personnel and must comply with protocol-specified criteria. Complete drug accountability records must be maintained. All records and undispensed supplies of the investigational product must be available for inspection during every monitoring visit for the conduct of AM0010 investigational product accountability and inventory. Please see the Pharmacy Manual for complete details.

5.1 Treatment Administration

5.1.1 AM0010

AM0010 is provided as a sterile, clear solution formulated at a concentration of 2 mg/mL and 4 mg/mL.

The AM0010 drug product is stored at the pharmacy at 2°C to 8°C. Patients will store their AM0010 in their refrigerator (2°C to 8°C).

While receiving FOLFOX during Cycles 1–12, AM0010 5 µg/kg will be administered as 1 of 2 fixed doses, either 0.4 mg for patients weighing ≤80 kg or 0.8 mg for patients weighing >80 kg.

AM0010 will be administered as a fixed dose, bracketed in 2 weight groups. Ongoing PK analysis has shown that the apparent clearance is proportional to weight supporting a weight-based dosing.

The rationale for dosing at a flat rate with a cutoff at 80 kg is based on safety and on the PK/Pharmacodynamic relationship. More specifically, immune activation with AM0010 requires a serum trough of at least 1 ng/mL. This trough level is reached with actual doses of 2.5 µg/kg and higher. The MTD of AM0010 is 20 µg/kg. Following the bracketed fixed dosing regimen, all patients will receive between 5 and 10 µg/kg AM0010. This dose range correlated with a survival benefit in a Phase 1b study with AM0010 + FOLFOX in PDAC patients.

The effects of overdose with AM0010 and an antidote to overdose with AM0010 are unknown. Non-human primates have been exposed to 5-10 times the expected serum concentration in humans without acute adverse reactions.

For any subject experiencing AM0010 overdose, observation for any symptomatic side effects should be instituted and vital signs and biochemical and hematologic parameters should be followed closely

(consistent with the protocol or more frequently, as needed). Appropriate supportive management to mitigate adverse effects should be initiated.

After discontinuation of FOLFOX (ie, completion of the planned 12 cycles or unacceptable FOLFOX-related toxicity), the AM0010 dose at the 10- $\mu\text{g}/\text{kg}$ dose level will be administered as 1 of 2 fixed doses (ie, either 0.8 mg in 0.2 mL for body weight ≤ 80 kg or 1.6 mg in 0.4 mL for body weight > 80 kg), based on the patient's weight during the course of the study.

In 144 patients who received AM0010 monotherapy, the MTD was determined at 20 $\mu\text{g}/\text{kg}$ (Naing et al., 2016). Pharmacodynamic analysis indicates immune activation at 10 $\mu\text{g}/\text{kg}$ in a monotherapy setting.

Patients will be trained to self-administer AM0010 and will self-administer the dose throughout the study, starting with the first dose. The Investigator or a qualified designee must be present during administration of the first dose. A Dosing Diary must be kept by the patient with date and time of administration for dosing compliance monitoring. The diary will be a part of the source documentation and should be reviewed with the patient at every visit. Note that if the patient is unable or unwilling to self-administer the SQ injection of AM0010, the dose may be given by a caregiver.

5.1.2 FOLFOX Administration

FOLFOX treatment will be continued for up to 12 cycles or until disease progression or unacceptable chemotherapy-related toxicity. The FOLFOX dosing regimen will consist of *dl*-LV 400 mg/m^2 and oxaliplatin 85 mg/m^2 followed by bolus 5-FU 400 mg/m^2 and a 46- to 48-hour infusion of 5-FU 2400 mg/m^2 . Note: if the institution is using l-LV (non-racemic), the dose is 200 mg/m^2 .

Prior to and during the treatment with either oxaliplatin or 5-FU at the beginning of each treatment cycle, premedication may be given per institution standard for the prophylaxis of nausea, vomiting, and diarrhea or following the guidelines below.

A 5-hydroxytryptamine-3 (5-HT₃) antagonist (eg, ondansetron or granisetron) and dexamethasone may be administered for the prophylaxis of nausea and vomiting. Dexamethasone (10 to 20 mg) may be administered as an IV bolus administered over 30 to 60 seconds.

For preparation and complete prescribing information, refer to the most current prescribing information in the region. Immune and chemotherapy regimens should be applied following the

guidelines in the protocol or established institutional practices. Investigators or designees will review the patient's hematology and chemistry panels, liver function tests, and the incidence of hematologic and non-hematologic toxicities prior to and during chemotherapy regimens.

5.1.3 Dosing Schedule

Patients will be treated on an outpatient basis with AM0010 plus FOLFOX or FOLFOX alone. Each cycle is 14 days.

ARM 1: AM0010 plus FOLFOX

[figure not shown]
AM0010 dose should be administered on Days 1–5 and Days 8–12 in the morning, ideally with 24 hours (± 2 hours) between doses. Days 6, 7, 13, and 14 will be rest days. FOLFOX dosing should be initiated on Day 1 of each cycle, after AM0010 administration on investigational ARM 1 (Figure 7). ARM 2 consists of FOLFOX administration alone as shown below, initiated on Day 1 of a 14-day cycle (Figure 8).

For patients in the combination therapy (AM0010 + FOLFOX) arm, after the last scheduled chemotherapy cycle in the absence of tumor progression, up to 12 cycles, or chemotherapy intolerance, maintenance dosing of AM0010 may continue 5 days on and 2 days off at 10 $\mu\text{g}/\text{kg}$ SQ qd (see Section 5.1.1).

Crossover of patients from the FOLFOX-only treatment arm into the FOLFOX plus AM0010 treatment arm is not permitted. Supportive care per the institution's normal standard of care, including concomitant medications, can be provided at the Investigator's discretion.

[figure not shown]
The documentation of the investigational product administration will be noted on the CRF page and in the source documentation. The date, dose volume, and time of administration for each dose will be recorded in the patient diary and on the respective CRF page. Details of preparing and administering AM0010 will be provided to the patient and are included in the Pharmacy Manual.

Figure 7: ARM 1: AM0010 + FOLFOX

ARM 1 in the absence of tumor progression may continue maintenance with AM0010 alone at either 0.4 mg for patients weighing ≤ 80 kg or 0.8 mg for patients weighing > 80 kg after completion of FOLFOX or FOLFOX intolerance

Figure 8: ARM 2: FOLFOX Alone

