2.2 Study Design

This is a randomized, open label, global Phase 3 Study of AM0010 in combination with FOLFOX compared with FOLFOX alone as second-line therapy in patients with advanced metastatic pancreatic cancer that has progressed during or following a first-line gemcitabine-containing regimen.

Approximately 566 patients will be randomized. Two interim analyses are planned. The first interim analysis will be performed when at least 60 randomized patients have had the opportunity to receive 4 months of therapy from the date of Randomization. Based on the first interim analysis, the Data Monitoring Committee (DMC) will review the PK exposure-safety and PK exposure-efficacy on the composite aggregate data for a Go/No-Go decision to enroll the entire Phase 3 study. The enrollment will continue during the analysis. The second interim analysis will occur when approximately 276 deaths (70% of total 393 deaths needed for final analysis) have occurred. Based on the second interim analysis, the DMC will recommend modifying, continuing the trial as planned, or discontinuing the trial.

Patients will be randomized in a 1:1 ratio to AM0010 combined with FOLFOX or FOLFOX alone.

The randomization will be stratified by 2 stratification factors:

- Prior single-agent gemcitabine therapy versus gemcitabine/nab-paclitaxel therapy
- North America versus Europe versus APAC.

Treatment Arms:

[figure not shown]
ARM 1: AM0010 (5 µg/kg) SQ dosed on Days 1–5 (with rest on Days 6 and 7) and Days 8-12 SQ (with rest on Days 13 and 14) plus FOLFOX (*dl*-LV 400 mg/m² and oxaliplatin 85 mg/m² followed by bolus 5-FU 400 mg/m² and a 46- to 48-hour infusion of 5-FU 2400 mg/m²) initiated on Day 1 of a 14-day cycle, for up to 12 cycles or until disease progression by RECIST v.1.1.

While receiving FOLFOX during Cycles 1–12, AM0010 at 5 µg/kg will be administered as 1 of 2 fixed doses, either 0.4 mg for patients weighing ≤80 kg or 0.8 mg for patients weighing >80 kg.

Patients in ARM 1 may continue on maintenance cycles with AM0010 (as shown below). After discontinuation of FOLFOX in the absence of tumor progression (ie, completion of the planned 12 cycles or unacceptable FOLFOX related toxicity), AM0010 at 10 µg/kg will be administered as 1 of 2 fixed doses, either 0.8 mg patients weighing ≤80 kg or 1.6 mg for patients weighing >80 kg.

ARM 1: AM0010 plus FOLFOX, for up to 12 cycles or until disease progression by RECIST v.1.1.

Figure 4: ARM 1: AM0010 + FOLFOX

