6.3 ARM 1 Subsequent Cycles AFTER Discontinuation of FOLFOX

6.3.1 ARM 1 (Investigational) Maintenance Cycles after Termination of FOLFOX (Every 28 Days)

In the absence of tumor progression, after completion of up to 12 planned cycles of FOLFOX or discontinuation of FOLFOX due to toxicity, patients assigned to ARM 1 may continue on AM0010 monotherapy at 10 µg/kg (either 0.8 mg for patients weighing ≤80 kg or 1.6 mg for patients weighing >80 kg, administered 5 days on and 2 days off).

Dose reductions in maintenance are the same as in combination at 80% and 60% by altering dose schedule. The 80% dose is administered 4 days on and 3 days off and the 60% dose is administered 3 days on and 4 days off.

The numbering of cycles during maintenance treatment in ARM 1 will follow the convention of “Maintenance Cycles” with Maintenance C1D1 beginning after discontinuation of FOLFOX and start of monotherapy AM0010 as described above. Each Maintenance Cycle will be 28 days/4 weeks in duration.

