- ^c Patients will complete 2 instruments, the EORTC QLQ-C30 and EQ-5D-5L. Both instruments will be administered at baseline (Screening), Day 1 of every treatment cycle regardless of dosing (both during the FOLFOX regimen and during the maintenance cycles), at EOT, and at the follow-up visit 30 days after EOT. Both instruments should be administered together at the beginning of the study visit prior to any extensive contact or consultation with study site personnel, which may bias patient responses. The EORTC QLQ-C30 will be presented first, followed by the EQ-5D-5L.
- ^d Vital signs (pulse, blood pressure, respiratory rate, and temperature) will be collected after being seated or in a semi-recumbent position. Day 1 Treatment vital signs may be performed 1 day prior.

- ^c ECG will be performed in patients seated, semi-recumbent, or supine for at least 5 minutes. A 12-lead ECG should be performed at Screening and EOT (ARM 1 and 2), ARM 1 only at pre-dose Cycles 1, 2, 3, and 5; and on Day 13 on Cycles 1,2, and 4. Day 1 Treatment ECG may be performed 3 days prior.
- ^f Survival Status, every 8 weeks for the first 12 months then every 12 weeks thereafter.
- ^g In patients assigned to AM0010 and FOLFOX (ARM 1), 1 dose of 5 µg/kg AM0010 will be administered daily by SQ injection on Days 1–5 and Days 8–12 of each 2-week cycle. Rest days when AM0010 will not be administered are Days 6–7 and Days 13–14.
- ^h AM0010 study drug and Dosing Diary will be dispensed to patients for self/caregiver administration. The diary will be a part of source documentation and should be reviewed with the patient at every visit. See Pharmacy Manual.
- ⁱ FOLFOX; Day 1 of each 14-day cycle for 12 cycles: *dl*-LV 400 mg/m² and oxaliplatin 85 mg/m² followed by bolus 5-FU 400 mg/m² and a 46- to 48-hour infusion of 5-FU 2400 mg/m².
- ^j PK samples obtained in patients on ARM 1 and ADA samples obtained in patients on ARMs 1 and 2. Samples will be collected during Cycles 1 and 2, Days 1 and 13, Cycle 3 Day 1 only, Cycle 4 Day 13 only, Cycle 5 Day 1 only. ADA will also be collected at EOT and at follow-up visit 30 days after EOT. Blood samples for biomarkers (PD samples) are collected pre-dose on C1D1, C1D13, C2D13, C4D13, and EOT for patients on both arms. See Lab Manual for further details.

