10.1.1. Treatment Exposure

The following parameters will be summarized by treatment arm:

Overall Treatment:

- duration of treatment (months):
 - \circ Pegilodecakin: (last dose date first dose date+1)/ 30.4375
 - Any component of FOLFOX: (last dose date first dose date + 14)/30.4375
- number of cycles administered (patient with total number of cycles administered, 1 cycle, 2 cycles, 3 cycles, etc.)
- total number of cycles administered

The following parameters will be summarized (descriptive statistics) by study drug component within each treatment arm:

- total cumulative dose (mg for pegilodecakin and mg/m² for each FOLFOX drug component)
- total dose per cycle (dose intensity)
- relative dose intensity (%), summarized by descriptive statistics and by categories of [60%, 80%), [80%, 100%), [100%, 120%) and ≥120%, etc.

In ARM 1(Pegilodecakin + FOLFOX), pegilodecakin's will be treated up to 12 cycles with 4 mg/cycle (2weeks) for patients with weight \leq 80 kg and 8 mg/cycle (2weeks) for patients with weight >80 kg. After the 12 cycle, patient receiving benefit on ARM 1 can continue on maintenance cycle with double of the dose 8 mg/2 weeks for patients with weight \leq 80 kg and 16 mg/2 weeks for patients with weight >80 kg. Therefore the exposure will be summarized in the following categories:

- for FOLFOX, exposure will only be summarized up to 12 cycles.
- for Pegilodecakin:
 - Cumulative dose, total dose per cycle and relative dose intensity will be summarized up to 12 cycle prior to maintenance period and repeated within the maintenance period.
 - The duration of treatment, and number of cycle administered will be summarized across all treatment durations and repeated for the maintenance cycle.

The key parameters used to calculate dosing data are shown in Table JZGB.10.1:

Table JZGB.10.1.	Patient Exposure Prior to Maintenance Period
------------------	--

		FOLFOX		
Treatment	pegilodecakin	Oxaliplatin	Leucovorin	5- FU
Planned Dose intensity	4 mg/cycle (14 days) (≤ 80kg) 8 mg/cycle (14 days) (> 80kg)	85 mg/m ² per cycle(14 days)	400 mg/m ² per cycle (14 days)	2800 mg/m ² per cycle (14 days)
Cumulative dose	sum of the doses mg for pegilodecakin, or mg/m^2 for FOLFOX administered to a patient during the treatment period			
Actual Dose intensity	Cumulative dose/ duration of treatment (mg/2week)	ration of treatment (mg/m ² /cycle)		
Relative dose intensity (%)	Actual Dose intensity/planned dose intensity			

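### The protocol prints two maintenance doses of AM0010, 0.4/0.8 mg and 0.8/1.6 mg; only the higher pair matches the stated 10 µg/kg level and the SAP's planned dose.

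*Protocol*

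**What the plan says.** **Lower pair, 0.4 mg (80 kg or less) or 0.8 mg (over 80 kg).** The text attached to the Arm 1 figure in Section 5.1.3 of the protocol says that Arm 1 patients without progression "may continue maintenance with AM0010 alone at either 0.4 mg for patients weighing" 80 kg or less, with 0.8 mg above that weight. The same sentence appears in the synopsis (Study Design) and in Section 2.2 (Figure 4).

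**Higher pair, 0.8 mg or 1.6 mg.**

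- The synopsis body text gives 0.8/1.6 mg at the 10 µg/kg level.
- Section 2.2 body text has "either 0.8 mg patients weighing" 80 kg or less, and 1.6 mg above, again at 10 µg/kg.
- Section 5.1.1 has "either 0.8 mg in 0.2 mL for body weight" up to 80 kg, and 1.6 mg in 0.4 mL above.
- Section 6.3.1, the maintenance procedure section, gives 0.8/1.6 mg "administered 5 days on and 2 days off".
- The body of Section 5.1.3 itself says "maintenance dosing of AM0010 may continue 5 days on and 2 days off at 10" µg/kg and refers the reader to Section 5.1.1.
- SAP Section 6.3 gives 0.8/1.6 mg. SAP Section 10.1.1 says patients "can continue on maintenance cycle with double of the dose 8 mg/2 weeks" at 80 kg or less, and 16 mg per two weeks above.

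**Two places that do not help the reader.** The Schedule of Events marks the AM0010 row for the maintenance column, but its footnote g ("In patients assigned to AM0010 and FOLFOX (ARM 1), 1 dose of 5" µg/kg) describes only the two-week combination cycle and gives no maintenance dose. Section 5.1.1 also states: "Following the bracketed fixed dosing regimen, all patients will receive between 5 and 10" µg/kg, without limiting this to the combination phase.

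**The concern.** The 0.4/0.8 mg pair is exactly the dose given with FOLFOX in Cycles 1–12. Maintenance is meant to be twice that: Section 1.3.2 explains why 10 µg/kg was chosen. The wrong line sits in the section headed Dosing Schedule and again in the synopsis, both places where site staff are likely to look. The unqualified 5–10 µg/kg sentence in Section 5.1.1 and the silent footnote in the Schedule of Events could both seem to confirm the lower dose.

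AM0010 is self-administered and maintenance cycles last 28 days, so a wrongly dispensed dose could be repeated at home for a whole cycle. At stake are the treatment actually delivered in maintenance and the maintenance exposure tables, which would mix two dose levels for a reason unrelated to tolerability. The primary comparison of overall survival is not changed as a test.

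**Working it through.** **Inputs.** Lower pair 0.4/0.8 mg (protocol synopsis, 2.2 and 5.1.3, figure text). Higher pair 0.8/1.6 mg (protocol synopsis, 2.2 body text, 5.1.1 and 6.3.1; SAP 6.3). Weight cut-off 80 kg. Schedule 5 days on and 2 days off, so 10 doses per 14 days and 20 per 28-day maintenance cycle. Planned dose per two weeks, SAP 10.1.1: 4/8 mg in combination and 8/16 mg in maintenance.

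**Step 1. Reproduce the SAP's planned dose** (mg per dose × 10 doses).

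- Combination: 0.4 × 10 = 4 mg and 0.8 × 10 = 8 mg, as in the SAP.
- Maintenance, higher pair: 0.8 × 10 = 8 mg and 1.6 × 10 = 16 mg, as in the SAP.
- Maintenance, lower pair: 4 mg and 8 mg, so 4/8 = 8/16 = 50% of the SAP's plan in both weight bands.

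**Step 2. Compare with the stated 10 µg/kg level** (µg/kg = mg × 1000 / kg).

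| Weight (kg) | Lower pair (µg/kg) | Higher pair (µg/kg) |
|---|---|---|
| 40 | 10.0 | 20.0 |
| 50 | 8.0 | 16.0 |
| 65 | 6.2 | 12.3 |
| 80 | 5.0 | 10.0 |
| 81 | 9.9 | 19.8 |
| 100 | 8.0 | 16.0 |
| 160 | 5.0 | 10.0 |

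At the cut-off, 10 µg/kg × 80 kg = 0.8 mg. The higher pair delivers 10–20 µg/kg over 40–160 kg. The lower pair delivers 5–10 µg/kg, below 10 µg/kg at every weight in that range except 40 kg.

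**Step 3. Check the volumes in Section 5.1.1.** 0.8 mg / 0.2 mL = 4 mg/mL and 1.6 mg / 0.4 mL = 4 mg/mL, one of the two supplied strengths. The higher pair is therefore consistent down to the injection volume.

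**Step 4. Effect on the reported dose intensity.** The SAP divides cumulative dose by duration of treatment and then by the planned dose intensity, with duration for this drug counted as last dose date − first dose date + 1. For a patient of 80 kg or less with no missed doses, the last dose falls on day 26 of one 28-day cycle and on day 82 of three.

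- One cycle, lower pair: 20 × 0.4 = 8 mg; 8 / (26/14) = 4.31 mg per two weeks; 4.31 / 8 = 53.8%.
- One cycle, higher pair: 16 mg; 16 / (26/14) = 8.62; 8.62 / 8 = 107.7%.
- Three cycles, lower pair: 60 × 0.4 = 24 mg; 24 / (82/14) = 4.10; 4.10 / 8 = 51.2%.
- Three cycles, higher pair: 48 mg gives 102.4%.

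The departures from 50% and 100% arise only because the duration stops at the last dose and leaves out the final rest days. The lower pair falls below 60%, which is the deepest maintenance reduction in Section 6.3.1 and the lowest category bound listed in SAP 10.1.1. A toxicity reduction applied on top of it would give 0.8 × 50% = 40% or 0.6 × 50% = 30% of plan.

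**Step 5. How many patients could meet the conflict.** Only Arm 1 patients who reach maintenance. The documents do not give that share. If it is assumed to be 10–40% of 283, that is 283 × 0.10 = 28 to 283 × 0.40 = 113 patients. This counts patients exposed to the conflicting text, not patients misdosed.

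**The case against.** The strongest reply is that the intended dose can be found. Section 5.1.3 says 10 µg/kg and points to Section 5.1.1, which gives milligrams and volumes. Section 6.3.1, where maintenance is described, repeats them. The lower dose appears only in text attached to the Arm 1 figure. Preparation and administration details are in the Pharmacy Manual, which is not among the documents and may be correct. Nothing shows that a site dosed from the figure text. All of this stands, and it bears on how likely harm is. It does not remove the contradiction: the synopsis and Sections 2.2 and 5.1.3 each disagree with themselves, and a manual does not cure that.

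Two side points are fairly contested. Read in place, the 5–10 µg/kg sentence in Section 5.1.1 follows the combination dose and precedes the maintenance paragraph, so it is loose wording and not a second wrong dose. Footnote g is an omission, not a conflict. Both are still worth correcting, because each could reinforce the wrong reading.

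It is also true that SAP Table JZGB.10.1 covers the period before maintenance. Applying its formula to maintenance is an inference, supported by the SAP's statement that the dose-intensity summaries are repeated for that period. Finally, SAP Figure JZGB.6.1 is not shown in the text available, so only the SAP's written text can be confirmed as correct.

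**Conclusion.** The concern holds. Current protocol text gives two maintenance doses that differ two-fold, and the higher pair is the intended one: it alone fits the 10 µg/kg level, the injection volumes and the SAP's 8/16 mg per two weeks. Following the lower pair means half the planned maintenance dose, 5–10 instead of 10–20 µg/kg over 40–160 kg, and a reported relative dose intensity of roughly 51–54% instead of 102–108% for one to three full cycles.

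The harm is conditional on a site using the figure text, and is confined to Arm 1 patients in maintenance (28–113 patients under the assumed 10–40% share). Sample size, power, alpha and the overall survival test are unaffected. This should be corrected because it concerns the dose a patient is given.

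**What to change.** 1. In the maintenance line of the Arm 1 figure text in the synopsis, Section 2.2 (Figure 4) and Section 5.1.3 (Figure 7), replace 0.4 mg and 0.8 mg with 0.8 mg and 1.6 mg.
2. Add the maintenance regimen to Schedule of Events footnote g: 0.8 mg at 80 kg or less, 1.6 mg above 80 kg, 5 days on and 2 days off, in 28-day cycles.
3. In Section 5.1.1, limit the 5–10 µg/kg statement to the combination phase and to 40–160 kg, and state 10–20 µg/kg for maintenance over the same weights.
4. Notify sites of the corrected dose, and check maintenance dosing records for 0.4/0.8 mg given as the starting maintenance dose. Where it is found, identify those patients in the maintenance exposure summaries, so that a text-driven half dose is not read as a toxicity reduction.

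The cost is text corrections at five places in the protocol, a site notice and a records check. The design does not change. The SAP's written text already uses the higher dose and needs no change; look at its Arm 1 figure once to confirm that it agrees.
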